### 3.4 **Inclusion of Women and Minorities**

Both men and women and members of all races and ethnic groups are eligible for this trial.

## 4. **REGISTRATION PROCEDURES**

All subjects must be registered with the UF Health Cancer Center prior to participation in this trial. The participating site must fax or email the completed study specific eligibility checklist and registration forms, supporting documents and signed informed consent to the Coordinating Center. Unsigned or incomplete forms will be returned to the site. Once documents are received, the designated Research Coordinator will review them to confirm eligibility and to complete the registration process. If eligibility cannot be confirmed, the research coordinator will query the site for clarification or additional documents as needed. Subjects failing to meet all study eligibility requirements will not be registered and will be unable to participate in the trial.

## 5. **STUDY TREATMENT**

All subjects entering the screening phase will receive a unique subject number. This number will be used to identify the subject throughout the study. Subjects withdrawn from the study will retain their subject number.

### 5.1 **Treatment Schedule/Administration**

All participants will have unresectable, previously-treated squamous cell NSCLC who have previously been treated with a platinum doublet (or have refused such prior therapy); those who have a molecularly targetable genetic mutation in their tumor must have also received the appropriate specific therapy for that mutation.

Both men and women of all races and ethnic groups will be eligible for this trial. This study was designed to include women and minorities, but will not be designed to measure differences of intervention effects. Men and women will be recruited with no preference to gender. No exclusion to this study will be based on race. Minorities will be actively recruited to participate.

Eligible subjects will include those with radiographically-staged locally advanced or metastatic NSCLC who have received any prior therapy for the lesion(s). Patients who receive radiation therapy to any indicator lesion must have demonstrated progressive growth of the lesion to be assessable; be willing to use contraception; are neither pregnant nor lactating; are greater than 18 years old and have an anticipated life expectancy of at least 12 weeks; have normal end-organ function and limited comorbidities, and are able to provide written informed consent.

Upon confirmation of eligibility and provision of written informed consent, subjects will receive TAS-102 (Lonsurf®) at its FDA-approved dose and schedule, 35 mg/m^2 up to a maximum of 80 mg per dose (based on the trifluridine component) orally twice daily within one hour of completion

of morning and evening meals on Days 1 through 5 and Days 8 through 12 of each 28-day cycle until disease progression or unacceptable toxicity. Doses will be rounded to the nearest 5 mg increment. Additional doses will not be taken to make up for missed or held doses. Subjects will be monitored weekly during the first cycle for tolerance, and tumor status will be assessed every other cycle. Participants will continue on therapy until the development of unacceptable toxicity, disease progression, or participant desire to discontinue protocol therapy. There is no set maximum of cycles, as patients who have responded and who are tolerating this regimen may continue it until withdrawal of consent, disease progression, development of undue toxicity, or death.

Those whose disease is responding systemically but who develop CNS metastases as their only site of progression will have protocol therapy temporarily held for the delivery of brain radiotherapy (whole brain and/or gamma knife) and then resume protocol therapy.

## 5.2 Concomitant Therapy

Relevant medical history should be obtained at screening and include prior medications and treatment history. All medications taken within 3 weeks prior to screening, regardless of indication, should be recorded

Use of any additional anti-neoplastic or anti-tumor agents not part of the study therapy, including chemotherapy, radiation therapy, immunotherapy, and hormonal anticancer therapy; these are not permitted while participating in this study. TAS-102 had minimal or no effect on the QTc interval; the drug was administered to 42 patients with advanced solid tumors with the recommended dosage regimen, but it had no large effect (i.e. > 20 ms) in the mean QTc interval when compared to placebo and no evident exposure-QT relationship was identified. Two of 42 patients (4.8%) had QTc greater than 500 msec and 1 of 42 patients (2.4%) had a QTc increase from baseline greater than 60 msec. The components of TAS-102 is not metabolized by the cytochrome P450 system, thus strong CYP inhibitors or inducers are not expected to have any effect on the metabolism of this drug. Study participants may receive additional investigational antineoplastic therapies upon completion of their participation in this protocol. Use of concurrent investigational agents is not permitted.

Any therapy or medication (except study drugs), administered from screening until 28 days after the last dose of either study drug, is considered a concomitant therapy or medication. However, if another course of anti-cancer therapy is initiated prior to the 28-day follow-up period visit; a record of concomitant medications will no longer be performed. If the use of any concomitant treatments (medications or procedures) becomes necessary, the treatment must be recorded, including the name of the drug or treatment, dose, route, date, indication for use, expected duration, and frequency of treatment. Assessment and documentation of concomitant medications will be done at each visit.

Subjects are prohibited from receiving the following therapies during the Screening and Treatment Phase of this trial:

- Antineoplastic systemic chemotherapy or biological therapy
- Immunotherapy not specified in this protocol

- Chemotherapy not specified in this protocol
- Investigational agents other than the study drug in this trial
- Radiation therapy

*NOTE: Radiation therapy to a symptomatic solitary lesion may be considered on an exceptional case by case basis after consultation with sponsor-investigator. The subject must have clear measurable disease outside the radiated field. Administration of palliative radiation therapy will be considered clinical progression for the purposes of determining PFS.*

Live vaccines within 30 days prior to the first dose of trial treatment and while participating in the trial. Examples of live vaccines include, but are not limited to, the following: measles, mumps, rubella, chicken pox, yellow fever, rabies, BCG, and typhoid (oral) vaccine. Seasonal influenza vaccines for injection are generally killed virus vaccines and are allowed. However, intranasal influenza vaccines (e.g. Flu - Mist®) are live attenuated vaccines, and are not allowed.

### 5.3 Dose Modifications

The National Cancer Institute (NCI) Common Toxicity Criteria for Adverse Events Version 4 (CTCAE) will be used to grade toxicity (<http://evs.nci.nih.gov/ftp1/CTCAE/About.html>).

The starting dose of TAS-102 is 35 mg/m^2 up to a maximum of 80 mg per dose (based on the trifluridine component) orally twice daily within one hour of completion of morning and evening meals on Days 1 through 5 and Days 8 through 12 of each 28-day cycle until disease progression or unacceptable toxicity. Doses will be rounded to the nearest 5 mg increment. Study medication will be administered on a 4 week schedule. Doses will be delayed or reduced for clinically significant (Grade 3-4) hematologic and non-hematologic toxicities that are related to protocol therapy according to the guidelines shown in the Dose Delays/Dose Modifications table that follows. Dose modifications will follow predefined dose levels. Dose adjustments for hematologic toxicity are based on the blood counts obtained in preparation for the day of treatment.

#### 5.3.1 Dose Modification Table

Dose level 0 (standard starting dose)	35 mg/m  po bid
Dose level – 1	30 mg/m  po bid
Dose level – 2	25 mg/m  po bid

Inpatient dose reduction and dose interruption will be permitted once a patient has experienced drug-related toxicity provided that the criteria for patient withdrawal from study treatment have not been met. All inpatient dose reductions are relative to the lowest dose of the current cycle.

For all toxicities, doses of TAS-102 will be modified based upon Day 1 and Day 15, complete blood cell counts. Day 1 TAS-102 dosing for each cycle will be held until:

- Absolute neutrophil count (ANC) is greater than or equal to 1,500/mm^3 or febrile neutropenia is resolved

- Platelets are greater than or equal to 75,000/mm^3
- Grade 3 or 4 non-hematological adverse reactions are resolved to Grade 0 or 1

Within a treatment cycle, TAS-102 will be withheld for any of the following:

- Absolute neutrophil count (ANC) less than 500/mm^3 or febrile neutropenia
- Platelets less than 50,000/mm^3
- Grade 3 or 4 non-hematological adverse reactions

After recovery, resume TAS-102 after reducing the dose by 5 mg/m^2/dose (as above) from the previous dose level, if the following occur:

- Febrile neutropenia
- Uncomplicated Grade 4 neutropenia (which has recovered to greater than or equal to 1,500/mm^3, or baseline in subjects with benign ethnic neutropenia) or thrombocytopenia (which has recovered to greater than or equal to 75,000/mm^3) that results in more than 1-week delay in start of next cycle
- Non-hematologic Grade 3 or Grade 4 adverse reaction except for Grade 3 nausea and/or vomiting controlled by antiemetic therapy or Grade 3 diarrhea responsive to antidiarrheal medication

If a subject experiences more than one toxicity, dose reduction should be according to the toxicity with the highest grade. In the case of two or more toxicities of the same grade, the investigator may dose reduce according to that deemed most causally related to study treatment. If more than 3 dose reductions are required, TAS-102 will be discontinued. Do not escalate dose after it has been reduced.

### **5.3.2 Non- Hematologic Toxicity**

For Grade 3 and 4 toxicities, treatment should be withheld until the toxicity resolves to Grade 1 or less (or to baseline), then reinstated (if medically appropriate) at a one level dose reduction. Nausea and vomiting or diarrhea must persist at Grade 3 or 4 despite maximal medical therapy. All agents should be dose reduced in cases where either agent may be the cause of a given toxicity. Patients must meet pre-treatment laboratory criteria (as specified in the inclusion criteria) at Day 1 of each cycle to receive therapy administration. Patients will not be eligible for further treatment if resolution of toxicities requires a greater than 3-week delay in the start of the next cycle (five weeks from the start of the prior cycle).

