#### 6.2 **Criteria For Study Treatment Discontinuation**

A subject will be discontinued from protocol therapy under the following circumstances:

- Any adverse event which, in the Investigator's opinion, requires termination of the study medication.
- Disease progression, unless at the discretion of the principal investigator (in collaboration with any co-sponsors or collaborators) continued treatment with study drug is appropriate.
- Substantial non-compliance (>25% of missed doses accounting for delays and dose modifications per protocol or instructions from research team staff for AEs), with the requirements of the study.
- The patient presents with a beta-HCG test consistent with pregnancy. Pregnancy will be reported along the same timelines as a serious adverse event.
- The patient uses illicit drugs or other substances that may, in the opinion of the Investigator, have a reasonable chance of contributing to toxicity or otherwise interfering with results.
- The development of a second malignancy that requires treatment, which would interfere with this study.

- The patient is lost to follow-up.
- Interruption in study drug administration for greater than 21 days (see Dose Modification section).
- Development of an intercurrent illness or situation which would, in the judgment of the investigator, affect assessments of clinical status and study endpoints to a significant degree.

The Investigator will make every reasonable effort to keep each patient in the study unless it is in the patient's best interests to discontinue participation. If a patient is removed from the study or declines further participation, all End of Treatment evaluations should be performed if the patient is willing and able to be assessed. A description of the reason(s) for withdrawal from the study must be recorded on the case report form (CRF). The Investigator should also ensure that all patients are followed up for survival status after the Final Visit.

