### 6.4 **Study Discontinuation**

It is unlikely that the trial itself will require a premature termination. However the trial will be stopped prematurely (prior to completion of accrual, protocol therapy, and follow-up) for safety reasons if the therapy at Dose level 0 is intolerable in the first six patients, requiring dose reduction to Dose level -1.

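### Section 5.3.2 can be read to spare treatment-responsive Grade 4 vomiting or diarrhoea the dose reduction that Section 5.3.1 requires, and the two sections set different recovery thresholds

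*Combined protocol and SAP*

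**What the plan says.** Section 5.3 limits dose changes to clinically significant Grade 3–4 toxicities related to protocol therapy, handled "according to the guidelines shown in the Dose Delays/Dose Modifications table that follows". Two subsections then cover non-haematologic toxicity.

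**Section 5.3.1 (Dose Modification Table).** Drug is withheld within a cycle for any Grade 3 or 4 non-haematologic reaction. After recovery the dose drops by 5 mg/m² for a "Non-hematologic Grade 3 or Grade 4 adverse reaction except for Grade 3 nausea and/or vomiting controlled by antiemetic therapy" or Grade 3 diarrhoea that responds to antidiarrhoeals. Day 1 of each cycle is held until "Grade 3 or 4 non-hematological adverse reactions are resolved to Grade 0 or 1". The Day 1 blood-count thresholds are ANC 1,500/mm³ and platelets 75,000/mm³. A reduced dose is never raised again.

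**Section 5.3.2 (Non-Hematologic Toxicity).** For Grade 3 and 4 events, "treatment should be withheld until the toxicity resolves to Grade 1 or less (or to baseline"), and treatment is then reinstated, if medically appropriate, one dose level lower. The next sentence reads "Nausea and vomiting or diarrhea must persist at Grade 3 or 4 despite maximal medical therapy". Day 1 dosing also requires the inclusion-criteria laboratory values, which Section 3.2 sets at ANC 1,000/µL and platelets 100,000/µL.

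No text says which subsection prevails where they differ.

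**The concern.** Dosing instructions after severe toxicity should give one answer. Here the 5.3.1 exemption stops at Grade 3, while the 5.3.2 sentence puts Grades 3 and 4 under the same persistence condition. A site working from 5.3.2 could conclude that Grade 4 vomiting or diarrhoea that settles on treatment needs no reduction. A site working from 5.3.1 would reduce.

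The difference for that patient is 35 against 30 mg/m² twice daily. Because 5.3.1 bars re-escalation, a reduction is permanent. The choice also fixes the dose level under which later safety data are counted, since Section 11.4 summarises safety by dose level and fits dose-toxicity curves. Sections 4 and 12.2 speak of participating sites, so practice could differ between sites.

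The recovery thresholds raise a smaller question of the same kind. A patient back at a Grade 2 baseline may restart under 5.3.2 but stays held under the literal 5.3.1 text. Section 6.2 lists "Interruption in study drug administration for greater than 21 days" as a reason to stop protocol therapy.

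**Working it through.** The plan gives no figure to reproduce. The check is a case comparison, then a bound on the number of patients.

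**Step 1. The two sections side by side (drug-related events).**

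| Case | 5.3.1 | 5.3.2 | Result |
|---|---|---|---|
| Grade 3 nausea, vomiting or diarrhoea, controlled | hold, no reduction | no reduction; hold depends on the reading | reduction agrees |
| Grade 3 or 4, persisting despite treatment | hold, reduce | hold, reduce | agree |
| Grade 4 vomiting or diarrhoea, responds to treatment | hold, reduce | can be read as no reduction; hold depends on the reading | can differ |
| Grade 3–4, recovers to Grade 0–1 | may resume | may resume | agree |
| Grade 3–4, recovers to a Grade 2 baseline | Day 1 held | may resume | differ |

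The hold depends on the reading because the 5.3.2 sentence is incomplete. It directly follows the reduction instruction. If it qualifies the reduction only, both sections hold drug. If it also qualifies the hold, the hold differs too, including for controlled Grade 3 events on dosing days.

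**Step 2. Bound for the reduction.** Inputs from the Section 9.1.9 table, Grade 3 or higher: diarrhoea 23/646 and vomiting 15/646 on TAS-102; 1/322 each on placebo.

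- Ceiling: (23 + 15)/646 = 38/646 = 5.9%; × 30 = 1.8 patients.
- Less placebo, as a proxy for drug-related events: 2/322 = 0.6%; 5.9% − 0.6% = 5.3%; × 30 = 1.6 patients.
- Floor: 0, because the table does not separate Grade 4 and no treatment-responsive fraction is given.

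The ceiling assumes that no patient had both events and that every event was Grade 4 and responded to treatment.

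**Step 3. Bound for the hold.** Adding nausea (15/646): (23 + 15 + 15)/646 = 53/646 = 8.2%; × 30 = 2.5 patients. This applies only if the sentence also qualifies the hold; otherwise it is 0. Nausea is left out of Step 2 on the assumption that the Grade 4 question concerns vomiting and diarrhoea. If it were counted there, 2.5 would be the ceiling for the reduction too.

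**Step 4. Dose step.** (35 − 30)/35 = 14%.

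**Step 5. Recovery to baseline.** Section 3 does not cap the baseline grade of symptoms, so a Grade 2 baseline is possible. The documents give no frequency, so no count is computed.

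**Step 6. Day 1 blood counts.** 5.3.1 is stricter on neutrophils (1,500 against 1,000) and 5.3.2 is stricter on platelets (100,000 against 75,000). Meeting both means ANC 1,500 and platelets 100,000, a pair that neither section states.

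The 5.3.2 delay limit is not used. It allows three weeks, but its parenthesis ("five weeks from the start of the prior cycle") means 5 − 4 = 1 week with 28-day cycles.

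**The case against.** The strongest reply is that the sections can be followed together. Section 5.3.2 does not forbid a reduction after a controlled Grade 4 event, and its restart is conditional on medical judgement. A site that reduces and waits for Grade 0–1 breaches neither section. Section 5.3 points to the table, and 5.3.1 carries that title. Section 5.3.2 also speaks of several agents in a single-product trial, which suggests carried-over text (an inference). All of this stands, and it favours 5.3.1. It does not settle the matter, because 5.3.2 is a numbered rule for exactly this toxicity and nothing subordinates it.

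A second reply is that the sentence has no consequence clause. That stands. A reader might infer that the sections flatly contradict each other on two points. The documents support less: an unclear sentence that can be read to relax the reduction.

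Third, the baseline question is narrow. It needs a Grade 2 symptom at entry that worsens to Grade 3–4 and settles back at Grade 2. Section 5.1 asks for normal end-organ function and limited comorbidities, which shrinks the pool. Section 10.1.1 defines an adverse event as something new or worse, so a site might reasonably treat baseline as resolution. This stands as to size. However, 5.3.1 names baseline explicitly for benign ethnic neutropenia, so its absence from the non-haematologic item is hard to read as implied.

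**Conclusion.** The point holds as a minor to moderate internal inconsistency. After a treatment-responsive Grade 4 event, a site using 5.3.2 could resume at full dose where 5.3.1 requires a 14% reduction. Between 0 and about 1.8 of 30 patients would be affected, and the true number may well be 0. The ceiling takes the Section 9.1.9 rates as applicable to this population, together with the assumptions in Step 2. The recovery-threshold difference is secondary and probably rare.

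Two further inferences are tempting and not supported. One is an effect on the response decision at 14 or 30 patients; nothing in the documents links a single dose level in so few patients to that outcome. The other is an effect on the Section 6.4 safety stop, which applies if therapy is "intolerable in the first six patients, requiring dose reduction to Dose level -1". At most 38/646 × 6 = 0.35 such events are expected among six patients, and the rule also requires intolerability, so an effect is possible but cannot be claimed.

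**What to change.** Make one wording amendment to Section 5.3:

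- State that, for non-haematologic toxicity, the hold and reduction rules of 5.3.1 control.
- Delete the persistence sentence in 5.3.2. Replace the first sentence of 5.3.2 with: *For Grade 3 and 4 toxicities, hold and reduce as in 5.3.1; reinstate only if medically appropriate.*
- Use one recovery threshold in both sections, Grade 0–1 by default. Add *or baseline* only if the investigator chooses it, since that loosens a hold rule and is a clinical decision the documents do not settle.
- Make the Day 1 laboratory criterion in 5.3.2 agree with the 5.3.1 values. Check 5.3.3 against the result, because it also refers to the inclusion values for recovery of counts.

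Controlled Grade 3 nausea, vomiting or diarrhoea would then be held and resumed without reduction, and Grade 4 would be held and reduced.

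The cost is drafting and IRB review, with no added patients, visits or tests. The downside is that at most about 1.8 of 30 patients lose one dose level. If sites now read 5.3.2 as conditioning the hold, at most about 2.5 of 30 would be held who might have continued.

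### Sections 5.3.1, 5.3.2 and 11.4 set three different standards for releasing Day 1 dosing, and the 5.3.1 hold omits the benign ethnic neutropenia allowance

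*Combined protocol and SAP*

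**What the plan says.** Three places govern the start of a cycle.

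- **Section 5.3.1.** "Day 1 TAS-102 dosing for each cycle will be held until" the listed conditions are met. For counts these are "Absolute neutrophil count (ANC) is greater than or equal to 1,500" per mm³, with resolution of febrile neutropenia joined to it by an *or*, and "Platelets are greater than or equal to 75,000" per mm³.
- **Section 5.3.2.** "Patients must meet pre-treatment laboratory criteria (as specified in the inclusion criteria) at Day 1 of each cycle to receive therapy administration". The limits it points to are in section 3.2, item H: ANC at least 1,000/µL and platelets at least 100,000/µL, plus creatinine, bilirubin and calcium limits. Item H also lets subjects with benign ethnic neutropenia enrol after discussion with the principal investigator, and gives no ANC floor for them.
- **Section 11.4.** Before later courses begin, a return to baseline must be documented. The requirement is repeated for every patient who has had toxicity.

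No text ranks these three. Section 5.3.3 uses the inclusion limits as its recovery standard after myelosuppression, although it is not written as a Day 1 release rule.

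The dose-reduction bullet of 5.3.1 accepts neutrophil recovery to 1,500 "or baseline in subjects with benign ethnic neutropenia", and platelet recovery to 75,000. It applies to Grade 4 neutropenia or thrombocytopenia "that results in more than 1-week delay in start of next cycle". The allowance in that bullet does not appear in the Day 1 hold list of the same section.

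**The concern.** The two sets of count limits differ in opposite directions: 5.3.1 is stricter on neutrophils and 5.3.2 is stricter on platelets. A site working from 5.3.1 alone would treat at platelets of 75,000 to 99,999. A site working from 5.3.2 alone would treat at ANC 1,000 to 1,499. The drug is myelosuppressive: section 9.1.7 reports Grade 3-4 neutropenia in 38% and thrombocytopenia in 5%.

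The chosen limit fixes the restart date, and the restart date drives other rules. A delay beyond one week can trigger a dose reduction under 5.3.1. Treatment ends under 5.3.3 after a delay of more than 2 weeks, under 5.3.2 when resolution of toxicity "requires a greater than 3-week delay in the start of the next cycle", and under 6.2 after an interruption of more than 21 days. (That these stopping limits differ is a separate matter.) Similar patients could therefore be re-treated, delayed, reduced or stopped differently.

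The missing allowance is a second problem. A subject with benign ethnic neutropenia may be enrolled with a stable ANC below 1,500. From Cycle 2 the 5.3.1 hold, taken at its word, would never lift for that subject, and 6.2 would then end treatment.

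**Working it through.** The plan states no figure to reproduce; the check sets the rules side by side. Units agree, since 1/mm³ equals 1/µL.

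| Source | ANC | Platelets |
|---|---|---|
| 5.3.1 Day 1 hold | ≥1,500, or febrile neutropenia resolved | ≥75,000 |
| 5.3.2 through 3.2 H | ≥1,000, with an entry exception for benign ethnic neutropenia | ≥100,000 |
| 11.4 | subject's own baseline | subject's own baseline |

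**Joint minimum of 5.3.1 and 5.3.2, no febrile neutropenia.**
- ANC: max(1,500; 1,000) = 1,500. Gap: 1,500 − 1,000 = 500.
- Platelets: max(75,000; 100,000) = 100,000. Gap: 100,000 − 75,000 = 25,000.

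Any subject who meets 100,000 has already met 75,000, so the 5.3.1 platelet limit has no effect if both sections are obeyed.

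**Test cases.**
- ANC 1,200, platelets 150,000: 5.3.2 is met, 5.3.1 holds.
- ANC 1,800, platelets 85,000: the 5.3.1 hold lifts, 5.3.2 is not met.

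**Febrile neutropenia.** If its resolution is a true alternative to the ANC limit, a subject in whom it has resolved passes both sections at 1,000/100,000.

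**Effect of 11.4.** The baseline standard can be tighter or looser than the other two. Suppose baseline platelets were 150,000 and the Day 1 value is 105,000: 5.3.1 and 5.3.2 are met on platelets, but the count has not returned to baseline. Suppose baseline ANC was 1,200 and the Day 1 value is 1,200: 11.4 and 5.3.2 are met on ANC, 5.3.1 is not. So 1,500/100,000 is the joint limit of 5.3.1 and 5.3.2 only, not of everything in the protocol.

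**Benign ethnic neutropenia.** With a stable ANC of, say, 1,200, the condition ANC ≥1,500 is never true, and without febrile neutropenia the alternative does not apply. The literal hold does not end.

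**Restart dates (hypothetical counts).** Assume Grade 4 thrombocytopenia lasting no more than 7 days, which avoids the separate 5.3.3 reduction trigger; adequate ANC; next Day 1 due on day 29; platelets 80,000 on day 36 and 105,000 on day 43. Leave 11.4 aside.
- 5.3.1 alone: restart on day 36. Delay 36 − 29 = 7 days, not more than 1 week, so its bullet requires no reduction.
- 5.3.1 and 5.3.2 together: restart on day 43. Delay 43 − 29 = 14 days. If the thrombocytopenia is held to have caused all 14 days, the dose falls to 35 − 5 = 30 mg/m². That attribution is open, because the same bullet counts 75,000 as recovered, a level passed by day 36.
- If 100,000 is first reached on day 44: delay 44 − 29 = 15 days, beyond the 2-week limit of 5.3.3, whose own recovery standard is the inclusion limits.

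**The case against.** The strongest reply is that nothing here is impossible to follow. Both sections state necessary conditions in adjacent text, so a careful site obeys both and arrives at the stricter, safer pair. That is correct, and a reader who infers an outright contradiction goes too far. It does not settle the matter: obeying both makes 75,000 inoperative as a release limit, yet 5.3.1 uses 75,000 a second time as its platelet recovery level, so a site cannot tell whether the figure was meant to work. Nor does the joint pair deal with 11.4.

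One might also say that the 5.3.2 sentence sits under a non-hematologic heading and does not reach counts. But 5.3.3 points to the same inclusion limits for recovery from neutropenia and thrombocytopenia, and item H of 3.2 covers bone marrow expressly.

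On benign ethnic neutropenia, the opening of 5.3 ties delays and reductions to "hematologic and non-hematologic toxicities that are related to protocol therapy", and a stable benign count is not such a toxicity. The reduction bullet also accepts baseline. Entry of these subjects is a permitted exception after discussion, not a recruitment aim. All of this stands: the intent is clear, and what remains is a literal omission in one bullet. A reader might further infer that the hold blocks Cycle 1 for anyone enrolled at ANC 1,000 to 1,499, since it covers each cycle. The same scope text points the other way.

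Finally, a reader might infer that reductions to 30 mg/m² would follow from the conflict, or that the primary analysis is compromised. The first is arguable, as the restart example shows. For the second, the 20% response rate of interest and the 14- and 30-subject stages do not depend on the restart limits.

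**Conclusion.** The point holds as an internal inconsistency in a safety rule, and it should be fixed. Sections 5.3.1 and 5.3.2 differ by 500/µL on ANC and 25,000/µL on platelets, in opposite directions; 11.4 adds an undefined baseline standard; no order of precedence is given. Without febrile neutropenia, 5.3.1 and 5.3.2 are met together only at or above 1,500/100,000, which neither section states. The benign ethnic neutropenia omission is a drafting gap: followed literally it withholds drug indefinitely from an enrolled subject, against the evident intent.

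The conclusion rests on reading the 5.3.2 sentence as covering blood counts and the 11.4 sentences as operative conditions on restarting. The number of patients affected cannot be computed. The Grade 3-4 rates in 9.1.7 would give about 0.38 × 30 ≈ 11 and 0.05 × 30 = 1.5 patients if they carried over, but they do not say how many subjects would have Day 1 counts inside the gaps. Sample size and response threshold are unaffected.

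**What to change.** 1. Add "or baseline in subjects with benign ethnic neutropenia" to the ANC bullet of the 5.3.1 Day 1 hold.
2. State one Day 1 ANC and platelet release standard in 5.3.1 for Cycle 2 onward, and say that the 3.2 entry limits govern Cycle 1 Day 1. The default is the stricter pair, 1,500/100,000. Choosing 75,000 would lower the effective platelet limit by 25,000/µL and is a safety decision for the sponsor.
3. Have 5.3.2 refer to that standard for counts only, keeping its creatinine, bilirubin and calcium limits. Have the baseline sentences in 11.4 refer to it too, and match the platelet recovery figure in the 5.3.1 reduction bullet to it. This replaces the literal 11.4 requirement, so the amendment should say so.
4. If 5.3.3 is also pointed to this standard at 1,500, disclose that its ANC recovery level rises from 1,000 to 1,500.
5. Say whether resolution of febrile neutropenia is an alternative to the ANC limit or an additional condition.

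The cost is a wording amendment with no added patients, possibly with some longer delays at sites that had been using the looser limit. Calcium is not among the 12 chemistry items in the section 7.1 footnote, so keeping the Day 1 calcium limit means confirming that it is measured on Day 1 of each cycle.
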